#### 6.2.1.1 Erosion, Abrasion and Recession (EAR)

Teeth that will be peroxide bleached and that exhibit none of the dentition exclusion criteria for tooth DH, will be examined for signs of cervical EAR ([Addy et al., 2000](#)). Only teeth that demonstrate signs of EAR will be assessed further for DH.

#### 6.2.1.2 Modified Gingival Index (MGI)

The MGI is a non-invasive visual assessment of gingival health ([Lobene, 1986](#)). MGI will be assessed for teeth that will be peroxide bleached and that exhibit none of the dentition exclusion criteria for tooth DH and which show signs of EAR. MGI should be scored for the facial gingiva, directly adjacent to the area of exposed dentine only, as described below.

Score	Description
0	Absence of inflammation
1	Mild inflammation; slight change in color, little change in color; little change in texture of any portion of the marginal or papillary gingival unit.
2	Mild inflammation; criteria as above but involving the entire marginal or papillary gingival unit.
3	Moderate inflammation; glazing, redness, oedema, and/or hypertrophy of the marginal or papillary gingival unit.
4	Severe inflammation; marked redness, oedema and/or hypertrophy of the marginal or papillary gingival unit, spontaneous bleeding, congestion, or ulceration.

#### 6.2.1.3 Clinical Mobility

Clinical tooth mobility will be assessed for teeth that will be peroxide bleached and that exhibit none of the dentition exclusion criteria for tooth DH, which show signs of EAR and which have an MGI=0 directly adjacent to the exposed dentine only, using a modification of the Miller Index ([Laster et al., 1975](#)) as described below.

Degree	Description
0	No movement or mobility of the crown of the tooth < 0.2mm in a horizontal direction
1	Mobility of the crown of the tooth 0.2 - 1mm in a horizontal direction
2	Mobility of the crown of the tooth exceeding 1mm in a horizontal direction
3	Mobility of the crown of the tooth in a vertical direction as well.

#### 6.2.1.4 Evaporative (Air) Sensitivity Assessment (Schiff sensitivity score)

The Evaporative (air) Sensitivity Assessment will be assessed for teeth that will be peroxide bleached and that exhibit none of the dentition exclusion criteria for tooth DH, which show signs of EAR, which have an MGI=0 directly adjacent to the exposed dentine and which have clinical mobility = 0 only.

Property of Haleon- Confidential

May not be used, divulged, published or otherwise disclosed without the consent of Haleon

The examiner will apply an evaporative air stimulus by directing a maximum one second application of air from a dental air syringe to the exposed dentine surface from a distance of approximately 1 cm. The subject response will be scored using the Schiff Sensitivity scale immediately following the evaporative air stimulus. The Schiff Sensitivity scale is an examiner based index ([Schiff et al., 1994](#)) focusing on a combination of specific, observable, physical, behavioral and verbal responses from the subject as a result of the stimulation of exposed dentine, rather than solely an oral request from the subject to discontinue stimulation and may facilitate discrimination. The examiner will indicate the subject's response to the evaporative air stimulus, after the stimulation of each individual tooth, using the Schiff Sensitivity scale as below.

Score	Subject Response
0	Subject does not respond to air stimulation
1	Subject responds to air stimulus but does not request discontinuation of stimulus
2	Subject responds to air stimulus and requests discontinuation or moves from stimulus
3	Subject responds to stimulus, considers stimulus to be painful, and requests discontinuation of the stimulus

### 6.3 Efficacy Assessments

The following efficacy assessments will be performed by appropriately trained staff/clinical examiners, at the times and in the order defined in the Schedule of Events section of this protocol.

If in the opinion of the examiner a subject is between defined grades/scores, a conservative approach should be used to provide the final score. The same approach should be applied throughout the study to ensure consistency in the grading of the scores at all timepoints.

#### 6.3.1 Tooth Sensitivity Questionnaire

The tooth sensitivity questionnaire [including VAS and LMS] will be completed by the subject at the screening visit, at Visit 2 (prior to bleaching) to describe the overall tooth sensitivity experienced by the subject on that day. The questionnaire should then be dispensed to the subject to complete at home, in the evening, every day until they complete the study. Thus on the day of Visit 2 the subject should complete 2 questionnaires, one at site and one in the home. Thereafter the subject should complete 1 questionnaire per day at home.

Subjects will indicate whether they have felt tooth sensitivity during the previous 24 hours. Those who indicate they have not felt tooth sensitivity will not be required to complete the rest of the questionnaire. Subjects who indicate they did feel tooth sensitivity will complete the remainder of the questionnaire comprising the VAS, LMS and Bothersomeness numerical rating scale (NRS).

Subjects will rate their overall tooth sensitivity using a 100mm VAS with end anchors of 'No Sensitivity' to 'Extreme Sensitivity'.

The LMS apply psychophysical procedures (magnitude estimation and cross-modality magnitude matching) to condition specific descriptive words relevant to the subject's response ([Gracely et al., 1978](#)). The descriptive words are then aligned along a Visual Analogue Scale (VAS) at distances that reflect the psychological distances between words. These scales have been piloted and validated in a previously reported dentine hypersensitivity trials ([Heaton et al., 2013](#), [Mason et al., 2019](#)). The LMS will be used to rate the intensity, duration, tolerability

Property of Haleon- Confidential

May not be used, divulged, published or otherwise disclosed without the consent of Haleon

and descriptive quality of their tooth sensitivity using the four individual 100 millimetre (mm) LMS.

The study staff will measure the line segment marked-off in mm from bottom to top along the line (for LMS) and from left to right (for the VAS) and record this in the CRF.

The subject will also complete a NRS for bothersomeness for which the subject should circle an appropriate number on the scale.

All questionnaire data shall be recorded in the CRF upon return of completed questionnaire.

All questionnaire data shall be recorded in the CRF.

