## 4 STUDY POPULATION

### 4.1 Type and Planned Number of Subjects

Healthy volunteers of either sex and any gender, aged 18 – 65 years will be recruited who wish to have their teeth whitened and meet all the inclusion/exclusion criteria.

Sufficient subjects will be screened to randomize approximately 90 subjects (approximately 30 per treatment group) to ensure approximately 88 evaluable subjects complete the study (assuming a 2% dropout rate).

This study can fulfill its objectives only if appropriate subjects are enrolled. The following eligibility criteria are designed to select subjects for whom participation in the study is considered appropriate. All relevant medical and non-medical conditions should be taken into consideration when deciding whether a subject is suitable for this protocol.

Subject eligibility to participate in the clinical study should be reviewed and documented by an appropriate member of the investigator's study team before subjects are included in the study.

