### **7.3 Blinding and Randomization**

Subjects will be randomized into the study provided they have satisfied all subject selection criteria.

Subjects will be randomized to one of the study products with a 1:1:1 allocation ratio using an Interactive Response Technology (IRT). The randomization schedule will use a stratified randomly permuted block design. Stratification will be based on the clinically diagnosis of DH at -Screening (Yes/No). Approximately 45% (40-50%) of randomized subjects should have clinically-confirmed DH.

Study products will be provided to subjects in individual packs (cartons); each carton will contain overwrapped tubes of study product. The carton and tubes of study product will be labelled with the same unique container number. Subjects will be assigned to container numbers associated with cartons containing only their randomized study product using an Interactive Response Technology (IRT); product codes will not be used.

Returned study products should not be re-dispensed to any subject.

This study is described as examiner-blind (the clinical examiner will be blinded to the product received).

To ensure the examiner remains blinded throughout the study, staff involved in the preparation and dispensing of study products will work in a separate area.

Subjects will be instructed not to remove study products from the opaque bags provided/cartons outside of the dispensing room, while at the study site. Dispensing staff will not be involved in any efficacy/safety assessment procedures during the study.

Site staff, study statistician(s), data management staff and other employees of the sponsor and vendors acting on behalf of the sponsor, who may influence study outcomes will be blinded to the product allocation.

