### 8.2 Populations for Analysis

- The Safety population will comprise all randomized subjects who receive at least one dose of the study product. This population will be based on the product the subject actually received.
- The modified Intent-To-Treat (mITT) population will include all randomized subjects who complete at least one use of study product and have at least one VAS score for tooth sensitivity recorded during the tooth-bleaching period. This population will be based on the study product to which the subject was randomized. Any subject who receives a randomization number will be considered to have been randomized.
- The Per-Protocol (PP) population will include all randomized subjects who do not have any protocol deviations that could confound the interpretation of analyses conducted on the mITT.

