#### 8.3.1 Primary Endpoint Analysis

The modified Intent-to-Treat (mITT) population will be used for the primary analyses.

The primary endpoints are:

- Daily VAS scores collected through the study
- Daily LMS scores collected through the study
- Daily Bothersomeness scores collected through the study
- Daily number and % of subjects with a tooth sensitivity-free day through the study
- Daily number and % of subjects with analgesic used to alleviate tooth sensitivity through the study

Property of Haleon- Confidential

May not be used, divulged, published or otherwise disclosed without the consent of Haleon

Each endpoint will be summarized descriptively at Screening and Visit 2 (pre-bleaching) as well as by each relative day within the tooth bleaching and post-tooth bleaching period.

Days within the tooth-bleaching period will be relative to the Visit 2 [at home] result (day 1) up to and including the result recorded on the day prior to Visit 3. Days within the post-tooth bleaching period will be relative to the result following Visit 3 (at home) (day 1) and include any results up to and including the day of Visit 4. The daily mean ( $\pm$  SE) profiles of VAS, LMS and Bothersomeness scores across the study (clearly denoting each period) will be plotted by study product group.

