**When completing this form please consider your experience over the last 24 hours**

Have your teeth been sensitive ? Y/N     **If NO do not complete any further questions.**

Please make a single vertical mark at the point on the line which represents the degree of overall tooth sensitivity (eg twinges, pain and other sensations in your teeth) that you have experienced **over the last 24 hours**

[figure not shown]
No Sensitivity	_____	Extreme Sensitivity
-------------------	-------	------------------------

For Site use only: \_\_\_\_\_ mm     \_\_\_\_\_ Initials

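### No value is set for days answered 'No' to sensitivity and mITT needs a recorded VAS, so as written subjects with no sensitive bleaching day leave the primary population

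*Combined protocol and SAP*

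**What the plan says.** Section 6.3.1 has subjects first state whether they felt tooth sensitivity in the previous 24 hours. It continues: "Those who indicate they have not felt tooth sensitivity will not be required to complete the rest of the questionnaire". The example form in Section 9.10 is firmer: "If NO do not complete any further questions". On that form the VAS, analgesic, LMS and bothersomeness items all come after this instruction. Study staff obtain the VAS by measuring the subject's mark, so a skipped line yields no measurement.

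Section 8.2 limits mITT to randomized subjects who used the product at least once and "have at least one VAS score for tooth sensitivity recorded during the tooth-bleaching period". Section 8.3.1 states: "The modified Intent-to-Treat (mITT) population will be used for the primary analyses". It then says that daily mean "profiles of VAS, LMS and Bothersomeness scores across the study (clearly denoting each period) will be plotted by study product group". Section 8.3.2 models the same scores by MMRM and ANCOVA, with the screening score as covariate, and repeats each analysis for the post-bleaching period. Section 8.3.8 treats missing values as missing at random. No section assigns a score to a day answered 'No'.

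**The concern.** A blank on a 'No' day is a known absence of sensitivity. Nothing in the text tells the analyst to treat it that way. Three consequences follow if the wording is applied as it stands.

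1. A subject with no sensitive day during bleaching has no recorded VAS and leaves mITT, even if sensitive afterwards. This selects on a post-randomization outcome and removes the subjects who did best on it. It also reaches the sensitivity-free-day endpoint, because people who were sensitivity-free on every bleaching day are no longer counted.
2. Daily VAS, LMS and bothersomeness summaries and models describe severity on sensitive days only. Missing at random does not fit, because the score is blank exactly when sensitivity is absent.
3. The screening score comes from the same form. A subject answering 'No' at screening has no covariate and drops from a standard MMRM or ANCOVA fit. This happens before randomization, so it is not selection on outcome. It does cost precision, and it narrows the result to people already sensitive at screening.

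The analgesic item raises a related gap. Section 8.3.2 offsets its rate by all days with an answered Yes/No item. The denominator for "Daily number and % of subjects with analgesic used to alleviate tooth sensitivity through the study" is not stated.

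Section 2 sets no formal success criterion but looks for a directional advantage of the NovaMin dentifrice over the reference. The affected scores are three of the five primary endpoints.

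**Working it through.** The documents give no sensitivity rates, correlations or SDs. Every size below is therefore an assumption-based illustration.

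**(a) Loss from mITT.** Let *p* be the share of days answered 'Yes', *ρ* the within-subject correlation and *n* the number of evenings. Under a beta-binomial model, with a = p(1−ρ)/ρ and b = (1−p)(1−ρ)/ρ:

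- P0, the chance of no sensitive day = B(a, b+n)/B(a, b)
- sensitivity-free share within mITT = 1 − p/(1−P0)

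Take ρ = 0.3 and n = 7, with the positive control midway between the other two arms.

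| Arm | p | P0 | Excluded of 30 | Free days, all | Free days, mITT |
|---|---|---|---|---|---|
| Reference | 0.60 | 0.061 | 1.8 | 40.0% | 36.1% |
| Positive control | 0.525 | 0.095 | 2.9 | 47.5% | 42.0% |
| Test | 0.45 | 0.143 | 4.3 | 55.0% | 47.5% |

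About 81 of 90 remain (90 − 1.8 − 2.9 − 4.3). The reference-test difference falls from 15 points to 11.4.

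- Visit 3 falls at 7 ± 1 days. With 6 to 8 evenings, 1.5-2.2 (reference) against 3.8-4.9 (test) are excluded, and the difference is 10.9-11.7 points.
- For reference/test rates from 70/55% down to 40/25% and ρ from 0.2 to 0.5, 0.4-9.1 against 1.4-14.9 of 30 are excluded. The difference is then 12-47% smaller.
- With 50% in every arm and ρ = 0.3, each arm loses 3.3 of 30 and the loss is balanced.

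**(b) Daily profiles.** Suppose a latent normal score with mean μ and SD s, where 'No' means latent ≤ 0.

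- All-day mean ('No' = 0) = μΦ(μ/s) + sφ(μ/s)
- Sensitive-day mean = μ + sφ(μ/s)/Φ(μ/s)

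For s = 20 and μ = 10 (reference) and 4 (test), the all-day means are 14.0 and 10.1, a difference of 3.8 mm before rounding. The sensitive-day means are 20.2 and 17.5, a difference of 2.7 mm. Over reference means of −5 to 15, test 6 lower, and s of 15 to 25, the shrinkage is 12-30%.

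**(c) Screening covariate.** Section 7.3 states: "Approximately 45% (40-50%) of randomized subjects should have clinically-confirmed DH". If only those subjects answer 'Yes' at screening, 0.40 × 90 = 36 to 0.50 × 90 = 45 subjects have a covariate. The documents do not say how many others would answer 'Yes'.

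**(d) The two MMRM effects kept apart.** Simulation: 30 per arm, 14 of them with DH, 7 days, score = max(0, latent), between-subject and day-to-day SD 12 mm each, latent test effect −8 mm, random-intercept fit. Three settings were used: non-DH reference bleaching mean 5, 0 or 10; DH shift 10, 10 or 8; screening mean −8, −12 or 0.

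- 'No' = 0 everywhere: SE about 1.6-1.9 mm.
- Bleaching 'No' days blank, all screening scores kept: SE about 1.9 mm, estimate about 15-20% smaller.
- Subjects with no screening score also dropped: SE 2.6-3.3 mm, with 38, 30 and 52 of 90 kept.

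**(e) Conventions that change the figures.**

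- With bothersomeness 5 on sensitive days and rates of 60% against 45%, the mean difference is 0.15 × (5−1) = 0.60 with floor 1, and 0.15 × (5−0) = 0.75 with floor 0.
- If 6 subjects use analgesics on a day with 18 'Yes' answers and 30 answered forms, the daily figure is 6/18 = 33% or 6/30 = 20%.

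**The case against.** The strongest reply is that zero is the natural VAS value, since the left anchor is 'No Sensitivity', and that the team would use it. Section 8.3 allows clarification in the blinded data review documentation, and Section 8.2.1 settles exclusions there. Missing counts and reasons for exclusion would be reported, so any loss would be visible. 'No' days also feed their own primary endpoint, and incidence plus severity on sensitive days is a coherent descriptive pair. The primary analysis is descriptive.

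Much of this stands, and it limits the severity. It does not supply the rule. Zero is not obvious for bothersomeness, whose scale runs from 1 to 10, or for LMS, whose anchors are not visible in the text. Nor does it settle whether an assigned zero counts as recorded for mITT, and that condition affects the incidence endpoint too.

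Four stronger readings might be inferred, and the documents do not support them.

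- *A shortfall against the planned 88.* Section 4.1 randomizes about 90 "to ensure approximately 88 evaluable subjects complete the study (assuming a 2% dropout rate"). That is 90 × 0.98 = 88.2: evaluable completers after dropout, not an mITT target.
- *A large loss of MMRM precision from blank days.* In (d) the SE rise comes almost entirely from the missing screening covariate. The settings let only 45-68% of confirmed-DH subjects answer 'Yes' at screening, which is probably pessimistic given their positive air-stimulus response at that visit. With both effects together, the estimate moves by +4%, +16% and −7%, so there is no consistent shrinkage.
- *Blank days erase a benefit.* With 60% against 30% sensitive days, all at 30 mm, a 9 mm difference (18 − 9) does become 0. With 50% in both arms and 30 against 20 mm, 5 mm (15 − 10) becomes 10. The direction depends on how a product works.
- *The analgesic item is certainly gated.* That rests on item order in a form marked as an example. Section 6.3.1 lists the remainder only as VAS, LMS and the bothersomeness scale.

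**Conclusion.** The concern holds as a should-fix. The gate, the missing scoring rule and the recorded-VAS condition together define an mITT that excludes subjects with no sensitive bleaching day. This is more than missing detail, because the stated population rule, applied as written, selects on outcome. It would shrink a true difference in sensitivity-free days: 15 points to 11.4 in the illustrative case, or 12-47% over the range tried. Daily-profile differences would shrink by 12-30% under the latent-normal model. If only confirmed-DH subjects answer 'Yes' at screening, 36-45 of 90 keep a covariate.

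All sizes rest on assumed rates and models. If the products do not differ, the mITT loss is balanced. The documents do not show that the sponsor intends the literal reading, and no population is named for the VITA or DHEQ analyses. For the sensitivity models, mITT is only implied, by Section 8.3.3.

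**What to change.** Before unblinding, in Sections 8.2 and 8.3 or in the blinded data review documentation:

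- Define mITT by at least one answered daily Yes/No item during bleaching, in place of a recorded VAS.
- Score answered-'No' questionnaires (screening, Visit 2 and daily) as VAS 0 mm. Set LMS and bothersomeness at floors that the sponsor confirms and declares; for bothersomeness the scale minimum is 1.
- State how the skipped analgesic item counts on a 'No' day, for example as no analgesic use for sensitivity, so that the daily percentage matches the offset in the rate model.
- Apply missing at random only where the Yes/No item itself is unanswered.
- Report sensitive-day-only scores as a labelled supplementary summary.

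The cost is a few sentences and no new data. The downside is more values at the floor, so the supportive non-parametric analysis foreseen in Section 8.3.2 is more likely to be needed. The LMS and bothersomeness floors remain choices, which is why they should be fixed while the data are still blinded.

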### **6.3.2 Whitening History and Post-Whitening Questionnaires**

Subjects will be dispensed the Whitening History and Post-Whitening Questionnaires to complete at . Subjects should complete these individually at the study site without reference to other subjects. Site staff should ensure the questionnaires are correctly completed before the subject leaves the site.

### **6.3.3 Dentine Hypersensitivity Experience Questionnaire (DHEQ)**

A 'short form' DHEQ-15 will be completed by each eligible subject at Visits 1, 2 (prior to first application of tooth bleaching), 3 and 4.

The DHEQ-15 is divided into two sections - Section 1 asks questions about 'your sensitive teeth and the impact it has on your everyday life'; Section 2 asks questions about 'the ways in which the sensations in your teeth affect you in your daily life' grouped into the following domains.

- Restrictions (Section 2, Q1-3)
- Adaptation (Section 2, Q4-6)
- Social Impact (Section 2, Q7-9)
- Emotional Impact (Section 2, Q10-12)
- Identity (Section 2, Q13-15)

At Visit 1 all questions will be answered - Section 1 (Q1-9) and Section 2 (Q1-15)

At Visits 2, 3 and 4 Section 1 (Q7-9 only) and Section 2 (Q1-15) will be answered.

### **6.3.4 Tooth Shade (Color) Assessment**

Tooth shade (color) of the facial surfaces of the facial surfaces of the anterior 6 maxillary and mandibular teeth (tooth numbers 6-11 and 22-27) will be assessed by a single, trained clinical examiner using the VITA Bleachedguide 3D-MASTER. The arch tooth position will be parallel to the floor.

Assessment conditions should be standardized: color corrected lighting in the range of 5000° Kelvin; a grey bib will be placed over the subject's clothing; subjects will be asked not to wear lipstick; assessments will be performed in the same room (necessary) at approximately the same time of day (if possible); outside light will be controlled by covering the windows or using a windowless room. Color determination should be made within 5-7 seconds of starting an assessment to avoid eye fatigue.

Property of Haleon- Confidential

May not be used, divulged, published or otherwise disclosed without the consent of Haleon

If required, the examiner will brush the subject's anterior teeth with a wetted toothbrush and/or floss to remove any debris which could impact the accuracy of the color assessment.

The VITA Bleachedguide 3D-MASTER ([Paravina, 2008](#)) uses a value-ranked ordered scale from 1 (the lightest) to 29 (the darkest). The shade level of each tooth surface is scored visually by the clinical examiner with reference to the Bleachedguide.

A single VITA Bleachedguide will be used for all assessments throughout the study wherever possible.

